- The recordings from these visits will be transcribed on a computer by a HIPAA-compliant transcription service.

Study Protocol

Patient Centered Support for Contraceptive Decision-Making: A Cluster Randomized Controlled Trial of a Contraceptive Decision-Support Tool

November 22, 2016

- After completing three visits, each provider will complete a survey about their demographic characteristics and the Maslach Burnout Inventory.

The procedure for patient participants is as follows:

- After being screened and consented by study staff, each patient will complete a short demographic survey (**Note:** This survey was not added to study procedures until 11/4/15, when a minor modification detailing it was approved) and have a family planning visit in the usual fashion as is performed at the clinic with providers participating in the study. As described above, the conversation between patient and provider will be recorded on a secure voice recorder during these visits, and the visits will be transcribed.

2. Randomization

After the pre-intervention phase and before the intervention phase, the provider participants will be randomized into intervention and control arms, stratified by clinic. Providers will be randomized using a random number table, clustered by each clinic. [name] will create a random number table using Stata 13's "ralloc" randomization module and blinded study IDs provided by study staff. The decision support tool intervention will then be introduced in a short orientation to the providers randomized to the intervention arm.

B. Intervention Phase Procedures

Study staff role: UCSF Research Assistants will track all recruitment activity using the clinic-specific Recruitment Tracking Log daily. Weekly totals will be tallied each Friday afternoon. At each recruitment shift in each clinic, there should be one UCSF Research Assistant (RA) who conducts eligibility and consent processes, and, if possible, one volunteer or Patient Stakeholder Representative who assists the RA with completing tracking logs, the time study, and managing iPads and other study equipment. Time study data will be collected in this phase the same as in the pre-intervention phase: patient arrival time, tool start and end time (if applicable), visit start time with clinician, and visit end time.

The procedure for provider participants is as follows:

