- Continuation of the chosen method seven months after her visit, without a gap of four consecutive weeks or more.
- **Secondary outcomes:**
 - Patient Contraceptive Counseling Satisfaction at post-visit survey
 - Factor analysis-validated survey created by the PI to assess patients' satisfaction with the contraceptive counseling experience.
 - Patient Chosen Contraceptive Method Satisfaction at the post-visit survey, and 4 and 7 months
 - 5-point Likert scale question regarding patient satisfaction with contraceptive method chosen.
 - Experience with Shared Decision-Making (measured at post-visit survey)
 - Patient report of having engaged in shared decision making with their provider and their experience with the decision making process, as well as qualitative coding of contraceptive counseling visits. The qualitative coding will focus on the presence or absence of shared patient-provider decision making and patient engagement in the decision making process, drawing on concepts from observational measures of shared decision making, as well as insights into the counseling process gained through our previous observational study.
 - Patient Decisional Conflict in Contraceptive Choice at the post-visit survey
 - Validated survey to assess patients' decisional conflict in medical decision making.
 - Patient Current Contraceptive Method Satisfaction at 4 and 7 months
 - 5-point Likert scale question regarding patient satisfaction with the contraceptive method they are currently using.
 - Patient Attitudes and Knowledge of Contraceptive Options and Features (post-visit survey)
 - Patient report of perceived knowledge of their options and questions derived from National Survey of Reproductive Contraceptive Knowledge and previous studies of contraceptive knowledge and attitudes.
 - London Measure of Unplanned Pregnancy at 4 and 7 months
 - Incidence of unplanned pregnancy among study participants.
 - Use of Any Moderately or Highly Effective Method of Contraception at 4 and 7 Months Follow-up
 - Whether patient is using an effective contraceptive method at 4 or 7 months follow-up survey.
 - Choice of a Highly Effective Method of Contraception at Baseline

Study Protocol

Patient Centered Support for Contraceptive Decision-Making: A Cluster Randomized Controlled Trial of a Contraceptive Decision-Support Tool

November 22, 2016

- Whether patient chooses a highly effective contraceptive method at baseline visit.

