	Pre-intervention	Post-intervention	Follow-up interview/recording (intervention arm only)
Demographics	X		
Provider burnout	X	X	
Provider/patient engagement in shared decision-making, measured qualitatively	X		X

B. Sample Size:

Specific Aim 1: We based our sample size calculation on our primary outcome, contraceptive continuation. Based on our previous studies in this population, we estimate that 50% of women in our control group will continue with their contraceptive method at seven months. Using this same data, we have calculated the intra-cluster correlation (ICC) of this response by provider and by clinic at ~0 and 0.021 respectively. Accounting for clustering and 20% loss to follow-up, as well as a inflation factor to account for differences in contraceptive initiation among those in clinics with IUDs and implants on-site as compared to those without these methods on site, a sample of 758 patients (approximately 32 patients for each of 24 providers) would provide 80% power in 2-sided tests with a type-I error rate of 5% to detect a 12 percentage point increase in continuation, to 62%. This difference in contraceptive continuation would be clinically meaningful and is consistent with effects reported in the contraceptive literature. Again using data from our previous study to estimate ICCs and baseline parameters, the sample will also provide 80% power to detect small-to-moderate but clinically significant differences in secondary outcomes as shown below.

Study Protocol

Patient Centered Support for Contraceptive Decision-Making: A Cluster Randomized Controlled Trial of a Contraceptive Decision-Support Tool

November 22, 2016

Outcome	ICC		Design effect	Baseline SD/%	SES/ MDD
	Clinic	Provider			
Continuous measures					
Decision conflict scale	0.000	0.027	1.3	1.9	0.25
Satisfaction score	0.152	0.075	1.7	6.5	0.31
Dichotomous measures					
Choice of highly effective method	0.096	0.000	0.9	23%	10.9%
Shared decision making	0.006	0.024	1.3	46%	14.3%
Unintended pregnancy	0.005	0.001	1.0	5%	-4.5%
For continuous outcomes, the standard deviation (SD) and standardized effect size (SES) are reported; for binary outcomes, the baseline prevalence and absolute effect, both in percent.					

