We will assess imbalance by treatment assignment using cross-tabulations and comparisons of within group means and medians. Inference for balance on provider covariates will use chi-squared, Fisher's exact, t, and Wilcoxon tests as appropriate, while differences in patient characteristics will be assessed using mixed effects models with fixed effects for clinic and random effects for provider. [IR-3] Primary analyses of treatment effects will be intention-to-treat, according to treatment assignment, and without regard to use of the tool or seeing an intervention provider. Treatment effects will be estimated using mixed effects linear, logistic, proportional odds, and multinomial models, with fixed effects for clinic and random effects for provider.

Missing data. [MD-1] Missing data will have been minimized by active follow-up of participants. [MD-4] Missing data rates for primary and secondary outcomes as well as important covariates will be reported, in combination with summaries of the reasons for missingness, including dropout and pregnancy. [MD-2] All analyses will handle missing data using 20-fold multiple imputation of missing outcomes, based on iterative chained equations. [MD-3] Summary effect estimates, averaged over the 20 imputed datasets, as well as confidence intervals and p-values, will be calculated using standard methods that account for imputation error.

Sensitivity analyses. [MD-5] Because informative missingness would violate the covariate-dependent missing at random (CDMAR) assumption of the standard multiple imputation procedure, we will conduct

Study Protocol

Patient Centered Support for Contraceptive Decision-Making: A Cluster Randomized Controlled Trial of a Contraceptive Decision-Support Tool

November 22, 2016

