 - Did not have a gap of 4+ weeks during which they were sexually active and did not use a Tier 1 or Tier 2 method at any point since enrollment for four weeks or more OR
 - Report that they discontinued the method at the time of their survey BUT are not using anything else, have not had sex since discontinuation and say they would use this method if they were to have sex (note: no participants met this criteria) OR
 - Never started the method but haven't had sex since enrollment and would use the method if they started having sex (note: no participants met this criteria)
- **Secondary outcomes:**
 - Patient Contraceptive Counseling Satisfaction at post-visit survey
 - Factor analysis-validated survey created by the PI to assess patients' satisfaction with the contraceptive counseling experience.

- In primary analysis, we will do top-scoring of the IQFP total score, i.e. a score of 55 versus all other scores
- Patient Chosen Contraceptive Method Satisfaction at the post-visit survey, and 4 and 7 months
 - 5-point Likert scale question regarding patient satisfaction with contraceptive method chosen.
 - In primary analysis, we will do top-scoring for this questions
 - **Note:** Slightly different questions at baseline and follow-up:
 - 1) Baseline: How satisfied are you with your choice of birth control today?
 - 2) 4mo and 7mo: how much you agree with statement “I chose the best method for me at the time”
- Experience with Shared Decision-Making (measured at post-visit survey)
 - Patient report of having engaged in shared decision making with their provider and their experience with the decision making process, as well as qualitative coding of contraceptive counseling visits. The qualitative coding will focus on the presence or absence of shared patient-provider decision making and patient engagement in the decision making process, drawing on concepts from observational measures of shared decision making, as well as insights into the counseling process gained through our previous observational study.
 - For the question regarding who made decision, we will collapse the responses into 3 categories
 - 1) Health care provider AND mostly health care provider
 - 2) Me and provider equally
 - 3) Mostly me AND me alone
 - For the question regarding whether the provider had a preference:
 - 1) “no preference” vs. other 4 categories

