 - For the 5-point Likert scale question regarding satisfaction with support provided/how the provider helped you to choose, we will do top scoring
 - For the question regarding satisfaction with involvement of provider in the decision making process, we will analyze using the existing three categories (no collapsing)
 - For the question regarding satisfaction with the degree to which provider expressed preference, responses will be collapsed into 3 categories:
 - 1) A lot less strongly AND less strongly
 - 2) Exactly right
 - 3) A little bit more strongly AND a lot more strongly
- Patient Decisional Conflict in Contraceptive Choice at the post-visit survey

- Validated survey to assess patients' decisional conflict in medical decision making.
 - In primary analysis, we analyze this scale as a continuous variable. We will dichotomize if this violates linearity assumptions.
- Patient Current Contraceptive Method Satisfaction at 4 and 7 months
 - 5-point Likert scale question regarding patient satisfaction with the contraceptive method they are currently using.
 - In primary analysis we will do top-scoring, i.e. a score of 5 versus all other scores
- Patient Attitudes and Knowledge of Contraceptive Options and Features (post-visit survey)
 - Patient report of perceived knowledge of their options and questions derived from National Survey of Reproductive Contraceptive Knowledge and previous studies of contraceptive knowledge and attitudes.
 - In primary analysis:
 - Will analyze each of these questions independently. For the questions related to effectiveness and the questions related to knowledge of IUDs, we will also analyze as either answering all questions correctly vs. answering any incorrectly, and also examine the number correct as an ordinal outcome.
 - For all knowledge and attitudes question, unless otherwise specified below, we will analyze answered correctly vs. incorrectly or I don't know
 - Emergency contraceptive knowledge question:
 - 1) Primary analysis: selection of emergency contraception AND copper IUD vs. not selecting both of those
 - 2) Sensitivity analysis: for having copper IUD in their answer vs. not
 - For the "Heard of" question: we are pre-specifying interest in responses regarding IUDs (analyzed together), implant, vasectomy, female sterilization, patch, and ring, with a primary interest in IUDs
 - 1) IUD primary analysis: heard of an IUD (either one) vs. not having heard of it
 - 2) Equivalent analyses for other methods

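### The protocol's own ICCs give about 72% power for decisional conflict and 67% for the continuous satisfaction score, not the stated 80%, and the secondary-outcome table cannot be reproduced as printed

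*Protocol*

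**What the plan says.** Protocol section VII.B (Specific Aim 1) sets the sample at 758 patients, "approximately 32 patients for each of 24 providers", on the primary outcome. It then states that "the sample will also provide 80% power to detect small-to-moderate but clinically significant differences in secondary outcomes as shown below". The table below that sentence lists five secondary outcomes with a clinic ICC, a provider ICC, a design effect, a baseline SD or percentage, and a detectable effect. It does not give the design-effect formula, the cluster size or the N behind the columns. The SAP has no sample-size section that would supply them.

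On the design, section III.A.2 says that "the provider participants will be randomized into intervention and control arms, stratified by clinic". Section VII.C estimates treatment effects with models "with fixed effects for clinic and random effects for provider".

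Both continuous outcomes are measured just after the visit; section VII.A lists, for example, "Patient Decisional Conflict in Contraceptive Choice at the post-visit survey". For decisional conflict the SAP says "In primary analysis, we analyze this scale as a continuous variable". For counselling satisfaction it says "In primary analysis, we will do top-scoring of the IQFP total score, i.e. a score of 55 versus all other scores".

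**The concern.** With about 32 patients per provider, a provider ICC of 0.027 should inflate the variance by more than 1.3, and one of 0.075 by much more than 1.7. If so, the 80% claim is wrong for those two rows. Aim 1 names the experience of counselling, including decisional conflict, so these are prominent secondary outcomes. A reader who relies on the table would judge a null result against a 20% chance of missing the listed effect, when the protocol's own inputs put that chance at about 28% and 33%. For satisfaction there is a further gap: power is given for a mean difference, but the planned analysis compares proportions.

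**Working it through.** **Inputs** (protocol VII.B unless noted). N = 758; 24 providers, 12 per arm; m = 758/24 = 31.58; two-sided 5%.

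| Outcome | ICC clinic | ICC provider | Printed design effect | Printed effect |
|---|---|---|---|---|
| Decisional conflict | 0.000 | 0.027 | 1.3 | 0.25 SD |
| Satisfaction | 0.152 | 0.075 | 1.7 | 0.31 SD |
| Highly effective method | 0.096 | 0.000 | 0.9 | 23% + 10.9 points |
| Shared decision making | 0.006 | 0.024 | 1.3 | 46% + 14.3 points |
| Unintended pregnancy | 0.005 | 0.001 | 1.0 | 5% - 4.5 points |

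**Formula.** Set total variance to 1. Randomisation within clinic and fixed clinic effects remove the clinic share. What remains, per patient, is m x ICC(provider) + [1 - ICC(clinic) - ICC(provider)], so

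DE = 1 - ICC(clinic) + (m - 1) x ICC(provider).

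For decisional conflict the clinic ICC is zero, and this is the standard 1 + (m - 1) x ICC.

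**Trying to reproduce the stated 80%.** Power = Phi(SES x sqrt(N/DE)/2 - 1.96). With the printed design effects at N = 758:
- conflict: Phi(0.25 x sqrt(758/1.3)/2 - 1.96) = 86%
- satisfaction: Phi(0.31 x sqrt(758/1.7)/2 - 1.96) = 91%

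Neither is 80%. At N = 606 (20% loss) they are 77% and 83%. The N that gives exactly 80%, (2 x 2.8016/SES)^2 x DE, is about 653 for conflict and 555 for satisfaction. Rounding does not close the gap. A common N needs a design-effect ratio of (0.31/0.25)^2 = 1.54 (1.43 to 1.65 with rounding), but the printed ratio 1.7/1.3 is 1.31 (1.22 to 1.40).

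**At the planned cluster size.**
- Conflict: DE = 1 + 30.58 x 0.027 = 1.826. Power = Phi(0.25 x sqrt(758/1.826)/2 - 1.96) = Phi(0.587) = 72.1%.
- Satisfaction: DE = 1 - 0.152 + 30.58 x 0.075 = 3.142. Power = Phi(0.31 x sqrt(758/3.142)/2 - 1.96) = Phi(0.448) = 67.3%.
- Detectable at 80% power, 2 x 2.8016 x sqrt(DE/N): 0.275 SD and 0.361 SD.

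**Sensitivity.**

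| Variant | Conflict | Satisfaction |
|---|---|---|
| Most favourable rounding of ICC and effect | 74% | 69% |
| No clinic subtraction | 72% | 65% |
| Assumed 5-10% loss | 70-71% | 66-67% |
| 20% loss (N = 606, m = 25.25, DE 1.655 and 2.667) | 67% | 65% |
| t on 24 - 4 - 1 = 19 df, N = 758 | 68% | 63% |
| t on 19 df, N = 606 | 62% | 60% |

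With 20% loss the detectable effects are 0.293 and 0.372 SD.

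**Binary rows.** Power = Phi(|p2 - p1| / sqrt(2 x DE x [p1(1-p1) + p2(1-p2)]/N) - 1.96). For shared decision making, DE = 1 - 0.006 + 30.58 x 0.024 = 1.728, and power = Phi(0.143/0.04716 - 1.96) = 86%. In the same way, highly effective method (DE 0.904) has 94% and pregnancy (DE 1.026) about 96%. Setting the ratio in this formula to 2.8016 gives differences detectable at 80% power and N = 758 of about 13.2, 8.6 and 3.6 points, against 14.3, 10.9 and 4.5 printed.

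**Where the printed design effects could come from.** With the formula above, m between 11.7 and 13.0 returns all five to one decimal; at m = 12.5 they are 1.31, 1.71, 0.90, 1.27 and 1.01. If the column is instead the square root of DE (a standard-error factor), m between 26.0 and 30.5 returns four of the five. The highly-effective-method row then gives sqrt(0.904) = 0.951, which prints as 1.0 rather than 0.9. On that scale the printed factors give 75% and 71% at N = 758.

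**The case against.** The strongest reply is that the documents state no formula, so any account of how the column arose is inference. This stands. A reader might infer that the table was built for about 12 patients per provider, in contradiction of the planned 32. The documents do not establish that. The square-root reading implies 26 to 30 per provider, close to the plan after some loss, and it fails in one row by 0.951 against a cut of 0.950. An unrounded provider ICC of about -0.0001 in that row would remove even that mismatch.

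A reader might also infer that the design-effect column alone is at fault. That does not follow either, because the printed effects do not come from the printed design effects at any one N. The highly-effective-method row shows this most simply: its provider ICC is zero, so its design effect is 0.904 at any cluster size, yet its printed difference has 94% power at N = 758 and 88% at N = 606. The square-root reading does not rescue the table: the two continuous rows would need more than 758 patients (about 849 and 944) and the highly-effective-method row far fewer.

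None of this restores the 80%. The shortfall uses only the printed ICCs, N, cluster size and effects, and no two-sided variant tried at the planned cluster size reaches 80%.

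Two further replies are fair. These are secondary outcomes, and the SAP promises estimates with confidence intervals, which show precision whatever the planned power was. The SAP also already reports some data, so the correction is to the record. Both points limit the weight of the concern without making the stated power correct.

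**Conclusion.** The 80% claim does not hold for the two continuous outcomes. At N = 758 the protocol's inputs give about 72% for decisional conflict and 67% for the continuous satisfaction score. These figures assume 1:1 allocation, equal cluster sizes, no loss at the post-visit survey and a normal reference. Loss or a t reference lowers them.

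Only the decisional conflict shortfall applies directly to a planned test. The SAP top-scores satisfaction, so for that outcome the main defect is that no power is stated for the analysis that will be run.

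The three binary rows err the other way at N = 758, with more than 80% power for their printed differences. Shared decision making is the tightest: 81% with 20% loss, and 77% if a t reference is also used.

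A reader might take this to mean that the trial is too small. The documents do not support that. The sample was set on the primary outcome, whose provider ICC is about zero, and its power is not affected by this point. The error should be corrected because it concerns outcomes named in Aim 1, but it is an error of reporting.

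**What to change.** Recompute the whole table in section VII.B, both design effects and detectable effects for all five rows, at the planned cluster size. State beneath it the formula, the m and N used, and whether the 20% loss is applied to post-visit outcomes.

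- Decisional conflict: restate as about 0.275 SD detectable at 80% power (0.29 SD with 20% loss).
- Satisfaction: replace the row with the detectable difference in the proportion scoring 55, using that binary outcome's prevalence and ICCs from the previous study. If the continuous score is also kept, state about 0.36 SD (0.37 SD with 20% loss).
- Binary rows: restate the differences so that they match 80% power at the stated N.

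The 80% sentence will then be true of the restated effects. The cost is one table, one sentence, and one prevalence and ICC estimate from the sponsor's existing data. The downside is that two stated figures become less favourable. Enrolment and the analysis do not change.

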Analysis Plan: Patient Centered Support for Contraceptive Decision-Making: A Cluster Randomized Controlled Trial of a Contraceptive Decision-Support Tool

Principal Investigator: [name] MAS

Intention-to-treat analysis

Participants who “cross over” from their assigned study arm (as determined by the provider they are likely to see) will be included in the final analyses in the arm in which they were initially assigned.

Modified intention-to-treat analysis: Post-randomization exclusion

Some participants may be excluded from analysis after being randomized:

- Participants who find out they are pregnant during their enrollment visit (and thus would have been ineligible had this been known prior to enrollment).
- Participants who enrolled in the study more than once (their second enrollment will be excluded).

Data Collection and Analysis

The outcomes of interest for this study have been divided into three specific aims, which dictate what type of data is collected and how it is analyzed.

Outcomes of Interest

Specific Aim 1: The primary outcome is a binary indicator of contraceptive continuation at 7 months and a secondary outcome is a binary indicator of contraceptive continuation at 4 months. For ambiguous cases for these outcomes, we used a blinded adjudication process and applied a standardized list of rules and assigned outcomes throughout the process of data collection. Potential outcomes for individuals are as follows: continuous users of chosen method, non-continuous users of chosen method, and missing but included and imputed.

For all variables, the analysis will use multiple imputation to deal validly with the missing values. Of note, specific variables were not collected from participants we collected data from more than 48 hours after their visit. Those variables will be analyzed in the same way as other missing outcomes.

- **Primary outcome:**
 - Continuation of the chosen method seven months after her visit, without a gap of four consecutive weeks or more. If participants completed a 4 month follow-up survey, they must have started their chosen method by the date of that survey to be considered continuous users. If they did not complete a 4-month follow-up survey and only completed a 7-month follow-up survey, they must have started their chosen method by 20 weeks post-enrollment (4 weeks after their 4-month follow-up milestone). Participants must be currently using their chosen method at the time of the 4-month follow-up survey to be considered continuous users, UNLESS they report this non-use as

part of a <4week gap at the time of the 7 month survey. Participants must be currently using their chosen method at the time of the 7-month follow-up survey to be considered continuous users.

- *Definition of continuation variable:* We will evaluate continuation based on the day of 7-month survey completion, within a 4-week window beginning 7 months after enrollment
- *Definition of chosen method:* In the primary analysis, continued use of any IUD among those choosing either IUD will be classified as continued use of the chosen method; we will conduct an additional sensitivity analysis in which only continued use of the type of IUD originally chosen will be classified as continuous.
- *Treatment of bridge method users:* For primary analysis, any combination of continuous bridge method use with or without subsequent use of the chosen method will be considered continuous; we will conduct a sensitivity analysis in which participants who never start their primary OR start their primary method after the 4-month follow-up survey are not considered continuous users of their chosen method.
- *Treatment of women who become pregnant.* Continuation at 7 months will be multiply imputed for participants who report a pregnancy before this point who had started their chosen method before 4 months and were continuing to use it at the time they became pregnant. Participants reporting discontinuation prior to pregnancy will be counted as non-continuers.
- *Continuous users of coitally-dependent methods:* For primary analysis, in addition to the standard definition of who is a continuous user of a chosen method, choosers of coitally-dependent methods will also be categorized as continuous users if they:
 - Did not have a gap of 4+ weeks during which they were sexually active and did not use a Tier 1 or Tier 2 method at any point since enrollment for four weeks or more OR
 - Report that they discontinued the method at the time of their survey BUT are not using anything else, have not had sex since discontinuation and say they would use this method if they were to have sex (note: no participants met this criteria) OR
 - Never started the method but haven't had sex since enrollment and would use the method if they started having sex (note: no participants met this criteria)
- **Secondary outcomes:**
 - Patient Contraceptive Counseling Satisfaction at post-visit survey
 - Factor analysis-validated survey created by the PI to assess patients' satisfaction with the contraceptive counseling experience.

- In primary analysis, we will do top-scoring of the IQFP total score, i.e. a score of 55 versus all other scores
- Patient Chosen Contraceptive Method Satisfaction at the post-visit survey, and 4 and 7 months
 - 5-point Likert scale question regarding patient satisfaction with contraceptive method chosen.
 - In primary analysis, we will do top-scoring for this questions
 - **Note:** Slightly different questions at baseline and follow-up:
 - 1) Baseline: How satisfied are you with your choice of birth control today?
 - 2) 4mo and 7mo: how much you agree with statement “I chose the best method for me at the time”
- Experience with Shared Decision-Making (measured at post-visit survey)
 - Patient report of having engaged in shared decision making with their provider and their experience with the decision making process, as well as qualitative coding of contraceptive counseling visits. The qualitative coding will focus on the presence or absence of shared patient-provider decision making and patient engagement in the decision making process, drawing on concepts from observational measures of shared decision making, as well as insights into the counseling process gained through our previous observational study.
 - For the question regarding who made decision, we will collapse the responses into 3 categories
 - 1) Health care provider AND mostly health care provider
 - 2) Me and provider equally
 - 3) Mostly me AND me alone
 - For the question regarding whether the provider had a preference:
 - 1) “no preference” vs. other 4 categories
 - For the 5-point Likert scale question regarding satisfaction with support provided/how the provider helped you to choose, we will do top scoring
 - For the question regarding satisfaction with involvement of provider in the decision making process, we will analyze using the existing three categories (no collapsing)
 - For the question regarding satisfaction with the degree to which provider expressed preference, responses will be collapsed into 3 categories:
 - 1) A lot less strongly AND less strongly
 - 2) Exactly right
 - 3) A little bit more strongly AND a lot more strongly
- Patient Decisional Conflict in Contraceptive Choice at the post-visit survey

- Validated survey to assess patients' decisional conflict in medical decision making.
 - In primary analysis, we analyze this scale as a continuous variable. We will dichotomize if this violates linearity assumptions.
- Patient Current Contraceptive Method Satisfaction at 4 and 7 months
 - 5-point Likert scale question regarding patient satisfaction with the contraceptive method they are currently using.
 - In primary analysis we will do top-scoring, i.e. a score of 5 versus all other scores
- Patient Attitudes and Knowledge of Contraceptive Options and Features (post-visit survey)
 - Patient report of perceived knowledge of their options and questions derived from National Survey of Reproductive Contraceptive Knowledge and previous studies of contraceptive knowledge and attitudes.
 - In primary analysis:
 - Will analyze each of these questions independently. For the questions related to effectiveness and the questions related to knowledge of IUDs, we will also analyze as either answering all questions correctly vs. answering any incorrectly, and also examine the number correct as an ordinal outcome.
 - For all knowledge and attitudes question, unless otherwise specified below, we will analyze answered correctly vs. incorrectly or I don't know
 - Emergency contraceptive knowledge question:
 - 1) Primary analysis: selection of emergency contraception AND copper IUD vs. not selecting both of those
 - 2) Sensitivity analysis: for having copper IUD in their answer vs. not
 - For the "Heard of" question: we are pre-specifying interest in responses regarding IUDs (analyzed together), implant, vasectomy, female sterilization, patch, and ring, with a primary interest in IUDs
 - 1) IUD primary analysis: heard of an IUD (either one) vs. not having heard of it
 - 2) Equivalent analyses for other methods
 - For the "How would you rate for yourself?" question, we interested in all methods (specifying IUDs and implants)
 - 1) All methods (specifying IUDs- IUD type analyzed separately- and implants)
 - 2) Continuous variable for all methods; 11 point scale
 - Effect on fertility question
 - 1) Marked either IUD as yes or I don't know vs. marked both IUDs as no

- 2) Marked anything other than Depo as yes or I don't know, vs. marked everything other than Depo no (we will not factor responses to the questions about Depo into this variable)
- London Measure of Unplanned Pregnancy at 4 and 7 months
 - Incidence of unplanned pregnancy among study participants.
 - Definition of unplanned pregnancy: LMUP < 10;
 - *Justification: Barrett 2004 Journal of Epidemiology and Community Health*
 - Use of Any Moderately or Highly Effective Method of Contraception at 4 and 7 Months Follow-up
 - Whether patient is using an effective contraceptive method at 4 or 7 months follow-up survey.
 - Definition of Moderately or Highly Effective methods: Tier 1 and Tier 2 methods
 - Choice of a Highly Effective Method of Contraception at Baseline
 - Whether patient chooses a highly effective contraceptive method at baseline visit.
 - Definition of Highly Effective methods: Tier 1
 - Primary analysis: all highly effective methods (IUDs, implants, female sterilization, vasectomy) vs. everything else
 - Sensitivity analyses:
 - All reversible highly effective methods (IUDs and implants) vs. everything else
 - Excluding patients who indicate that they had to pay out of pocket for their birth control method
 - Use of a Highly Effective Method of Contraception at 4 and 7 Months Follow-up
 - Whether patient is using a highly effective contraceptive method at 7 month follow-up survey.
 - Primary analysis: all highly effective methods (IUDs, implants, female sterilization, vasectomy) vs. everything else
 - Sensitivity analyses:
 - All reversible highly effective methods (IUDs and implants) vs. everything else
 - Excluding patients who indicate that they had to pay out of pocket for their birth control method
 - Continuation of the chosen method 4 months after her visit.
 - Continuation of the chosen method four months after enrollment, without a gap of four consecutive weeks or more. In order to be considered continuous users. If participants completed a 4-month follow-up survey, they must have started their chosen method by the date that survey to be considered continuous users. If they did not complete a 4-month follow-up survey and only

completed a 7-month follow-up survey, they must have started their chosen method by 20 weeks post-enrollment (4 weeks after 4-month follow-up milestone). Participants must be currently using their chosen method at the time of the 4-month follow-up survey to be considered continuous users, UNLESS they report this non-use as part of a <4week gap at the time of the 7-month survey.

- *Definition of continuation variable:* We will evaluate continuation based on the day of 4-month survey completion, within a 4-week window beginning 4 months after enrollment
- *Definition of chosen method:* For primary analysis, we will collapse IUD types for chosen method; we will conduct an additional sensitivity analysis in which we do not collapse IUD types
- *Treatment of bridge method users:* For primary analysis, any combination of continuous bridge method use with or without subsequent use of the chosen method will be considered continuous; we will conduct a sensitivity analysis in which participants who never start their primary OR start their primary method after 4mo follow-up survey are not considered continuous users of their chosen method
- *Treatment of women who become pregnant.* Continuation at 4 months will be multiply imputed for participants reporting a pregnancy before this point who had started their method and continued to use it until they became pregnant and for those who never started their method before their 4 month survey. Participants reporting starting and then discontinuing their chosen method prior to pregnancy will be counted as non-continuers.
- *Continuous users of coitally-dependent methods:* For primary analysis, in addition to the standard definition of who is a continuous user of a chosen method, choosers of coitally-dependent methods will also be categorized as continuous users if they:
 - 1) Did not have a gap of 4+ weeks during which they were sexually active and did not use a Tier 1 or Tier 2 method at any point since enrollment for four weeks or more (asked about a gap when were sexually active in the gap question) OR
 - 2) Report that they discontinued the method at the time of their survey BUT are not using anything else, have not had sex since discontinuation and say they would use this method if they were to have sex (note: no participants met this criteria) OR
 - 3) Never started the method but haven't had sex since enrollment and would use the method if they started having sex (note: no participants met this criteria)

Pre-specified covariates for patients for Specific Aim 1:

- Age
 - <20
 - 20-24
 - 25-29
 - 30-34
 - ≥35
- Parity
 - 0
 - ≥1
- Race/ethnicity
 - White
 - Black
 - Latina
 - Other
- Language
 - English
 - Spanish
- Parental education
 - ≤ High school
 - Some college
 - ≥ College

Pre-specified covariates for providers for Specific Aim 1:

- Age
 - <36
 - 36-50
 - ≥51
- Race/ethnicity
 - White
 - Other
- Professional Degree
 - NP
 - Non-NP

Specific Aim 2: Qualitative assessment of patient engagement and the presence of shared decision making between counseling provided before and after implementation of the decision support tool by providers randomized to the intervention group. As described above, the qualitative coding will focus on the presence or absence of shared patient-provider decision making and patient engagement in the decision making process, drawing on concepts from observational measures of shared decision making, as well as insights into the counseling process gained through our previous observational study.

Specific Aim 3:

- Qualitative assessment of providers' and staff members' experiences using interviews and focus groups
- Quantitative measures of consultation time and total clinic visit time
 - Total Clinic Visit Time
 - Total amount of time a patient spends in a clinic for a family planning visit, from check-in to check-out.
 - Time of visit end minus time of check-in (recorded in clinic tracking sheets)
 - Time Spent with Contraceptive Counseling Provider
 - Total amount of time spent with the provider that is providing contraceptive counseling.
 - Time of visit start minus time of visit end (recorded in clinic tracking sheets)
 - **Note:** this measurement will be different at PP Valencia because consultation time included time spent with RHS and clinician, rather than a singular contraceptive counseling provider as at other clinics
- Change in provider burnout, pre- and post-intervention, using the Maslach Burnout scale, measured prior to implementation of the intervention and at the end of the trial
 - Maslach Burnout Inventory:
 - Given to provider participants to measure emotional exhaustion, depersonalization, and personal accomplishment subscale scores.
 - In primary analysis, we will conduct 3 different analyses, with each subscale (emotional exhaustion, depersonalization, and personal accomplishment) as a continuous variable

Pre-specified covariates for providers for Specific Aim 3:

- Age
 - <36
 - 36-50
 - ≥51
- Race/ethnicity
 - White
 - Other
- Professional Degree
 - NP
 - Non-NP

Methods of Analysis

Patient and provider stakeholders will be involved in an iterative manner in all stages of planning of analyses and in data interpretation.

